10. IMPORTANT PROTOCOL DEVIATIONS

Important protocol deviations (IPDs) will be identified and documented based on data listings and the protocol deviations log; the data will be presented separately.

Unless otherwise specified, the IPD summary tables will include the following columns: SEP-363856 50 to 100mg/day.

The IPD categories may include, but may not be limited to:

- Did not satisfy inclusion and/or exclusion criteria.
- Received prohibited medication.
- Overall compliance rate <75% or >125%.

IPDs will be identified and presented in a data listing. The number and percentage of subjects within each IPD category will be summarized for the SAF population.

A dedicated listing will present protocol deviations related to COVID-19.

11. DEMOGRAPHIC AND OTHER BASELINE CHARACTERISTICS

Unless otherwise specified, the demographic and Baseline characteristics summary tables will include the column: SEP-363856 50 to 100 mg/day.

Demographic data and other Baseline characteristics will be presented for the SAF population, EFF population, and PP population. The data will be presented by the treatment group.

No statistical testing will be carried out for demographic or other Baseline characteristics.

The following demographic and other Baseline characteristics will be reported for this study.

Age (years) - calculated relative to date of informed consent; as a continuous variable

- Age (years) categories:

- <18 years

Document: PPD

Author: PPD

Version Number:

1.0

Version Date:

06MAY2024

- ≥18 to ≤40 years
 - >40 to ≤65 years
 - >65 years
- Age (years) categories for ClinicalTrials.gov (CTR.GOV):
 - ≤18 years
 - >18 to <65 years
 - ≥65 years
- Age (years) categories for European Union Drug Regulating Authorities Clinical Trials Database (EudraCT):
 - <12 years
 - ≥12 to <18 years
 - ≥18 to <65 years
 - ≥65 years
- Sex:
 - Female
 - Male
- Race:
 - American Indian or Alaska Native
 - Asian
 - Black or African American
 - Native Hawaiian or Other Pacific Islander
 - White
 - Multiracial
 - Other
- Ethnicity:
 - Hispanic or Latino
 - Not Hispanic or Latino

Document: PPD

Author: PPD

Version Number:

1.0

Version Date:

06MAY2024

- Country :
 - United States
- Baseline Height (cm), as a continuous variable
- Baseline Weight (kg), as a continuous variable
- Baseline BMI (kg/m²), as a continuous variable
- Baseline BMI (kg/m²) category:
 - Underweight: <18.5 kg/m²
 - Normal: ≥18.5 to <25.0 kg/m²
 - Overweight: ≥25.0 to <30.0 kg/m²
 - Obese: ≥30.0 kg/m²
- Baseline Waist Circumference (cm), as a continuous variable
- Baseline PANSS Total Score, as a continuous variable
- Baseline PANSS Total Score categories:
 - < Overall median Baseline value
 - ≥ Overall median Baseline value
- Baseline PANSS Subscale Scores, as continuous variables
- Baseline PANSS Subscale Score categories:
 - < Overall median Baseline value
 - ≥ Overall median Baseline value
- Baseline PANSS Positive vs Negative Subscale Score categories:

Document:

PPD

Author:

PPD

Version Number:

1.0

Version Date:

06MAY2024

- Positive Subscale Score < Negative Subscale Score
 - Positive Subscale Score ≥ Negative Subscale Score
- Patient type based on Baseline UPSM factor scores:
 - Type 1: Prominently Disorganized
 - Type 2: Prominently Negative
 - Type 3: Prominently Hostile
 - Type 4: Prominently Positive
 - Type 5: Prominently Affective
- Baseline CGI-S Score, as a continuous variable
- Baseline CGI-S Score categories:
 - <4
 - ≥4 to ≤5
 - >5
- Prior Antipsychotic Drug Administration
 - 1
 - 2
- Number of subjects who agreed to tokenization
- DSM-5 schizophrenia subtype diagnosis:
 - 295.90 Schizophrenia
 - 293.89 Schizophrenia with Catatonia
- Any other current psychiatric disorders:
 - Yes
 - No

Diagnosis and DSM-5 code for any other current psychiatric disorders will be summarized in a separate table. These other current psychiatric disorders will be coded using Medical Dictionary for Regulatory Activities (MedDRA) central coding dictionary, Version 22.0 or higher, and presented by System Organ Class (SOC) and Preferred Term (PT).

Document: PPD

Author: PPD

Version Number:

1.0

Version Date:

06MAY2024

11.1. DERIVATIONS

- BMI expressed in kg/m²:

Weight (kg)/ height (m)².

12. MEDICAL HISTORY

Unless otherwise specified, the medical and surgical history summary tables will include the column: SEP-363856 50 to 100 mg/day.

Medical and surgical history information, including both past and concomitant medical conditions and major surgical history, as collected on the "Medical History" CRF form, will be coded using MedDRA, Version 22.0 or higher, and presented by SOC and PT for the SAF population by the actual treatment group. Data will be sorted by SOC based on the internationally agreed order ([APPENDIX 4](#)) and by PT in decreasing frequency.

13. MEDICATIONS

Unless otherwise specified, the medications summary tables will include the following columns: SEP-363856 50 to 100 mg/day.

Medications will be coded to Anatomical Therapeutic Chemical (ATC) Levels and Preferred Names according to World Health Organization Drug (WHODRUG) dictionary, Version 01MAR2019 or later.

Whenever available, the time information should be accounted for in the derivation of prior, concomitant, and post-treatment medications. See [APPENDIX 2](#) for the handling of partial dates for medications. In the case where it is not possible to define a medication as prior, concomitant, or post treatment, the medication will be classified by the worst case; i.e., concomitant.

- Prior medications are medications which stopped prior to the first dose of study medication.
- Concomitant medications are medications which started at the same time of or after the first dose of study medication and at the same time of or before the last dose of study medication; or started prior to and ended at the same time of or after the first dose of study medication; or started at the same time of or prior to the last dose of study medication and marked as ongoing.
- Post-treatment medications are medications which started after the last dose of study medication.

Document: PPD

Author: PPD

Version Number:

1.0

Version Date:

06MAY2024

Prior and concomitant medication use will be summarized by ATC Level 3 and Preferred Base Name for the SAF population by the actual treatment group. Medications will be sorted by ATC Level 3 alphabetically and by Preferred Base Name in decreasing frequency in the "SEP-363856 50 to 100 mg/day" column. Similar summary for primary and secondary prior antipsychotic drug administration will also be presented separately.

Descriptive statistics of primary prior antipsychotic drug dosage at each visit will be presented. The number of subjects who complete the down tapering will also be presented by week.

Prior, concomitant, and post-treatment medications will be provided in data listings.

Psychotropic and/or Sedating Medications taken by subjects prior to each visit as collected on the "*Timing of last dose of Psychotropic and/or Sedating Medications*" CRF form will be summarized by ATC Level 3 and Preferred Base Name for the SAF population by the actual treatment group and visit.

14. STUDY MEDICATION EXPOSURE

Unless otherwise specified, the study medication exposure summary tables will include the column: SEP-363856 50 to 100 mg/day.

Exposure to study medication data will be summarized for the SAF population by the actual treatment group.

Duration of exposure (in days) will be summarized both as a continuous variable for the treatment period and categorically:

- Number and percentage of subjects with exposure $\geq 1, \geq 7, \geq 14, \geq 21, \geq 28, \geq 35, \geq 42, \geq 49$, and ≥ 56 days
- Number and percentage of subjects with exposure for 1 - 6, 7 - 13, 14 - 20, 21 - 27, 28 - 34, 35 - 41, 42 - 48, 49 - 55 and ≥ 56 days

Total person-years of exposure will be calculated for all subjects.

Mean daily dose and modal daily dose will be calculated for the treatment period and summarized.

The dose adjustment decision at each visit will be summarized in a shift table.

Lastly, the number of days that a subject received the 50 mg/day dose level, the 75 mg/day dose level and 100 mg/day dose level will be summarized for the SAF population both as a continuous variable and categorically:

- Number and percentage of subjects with exposure to a particular dose level for 1 - 6, 7 - 13, 14 - 20, 21 - 27, 28 - 34, 35 - 41, 42 - 48, 49 - 55 and ≥ 56 days

Document: PPD

Author: PPD

Version Number:

1.0

Version Date:

06MAY2024

14.1. DERIVATIONS

- Duration of exposure (days) = date of last dose of study drug – date of first dose of study drug + 1. Interruptions in exposure (i.e., missed doses) and dose changes (if any) are not considered in the calculation of overall exposure.
- Total person-years of exposure is the sum of all durations of exposure in days / 365.25.
- Mean daily dose (mg/day):

$$\frac{\sum \text{Dose per tablet for Visit } j * (\# \text{ Tablets Dispensed for Visit } j - \# \text{ Tablets Returned for Visit } j - \# \text{ Tablets Lost for Visit } j)}{\text{Duration of Exposure}}$$

If the number of tablets dispensed, returned, and/or lost as collected on the "Study Treatment Administration as Collected / Drug Accountability Log" CRF form is missing for one or more visits, the mean daily dose will be calculated based on visits with complete drug accountability data available. That is, the numerator of the formula above will only include visits with the number of tablets dispensed, returned, and lost available, and the denominator should be adjusted to exclude dosing periods covered by visits excluded from the calculation (i.e., Duration of Exposure – dosing periods [sum of (EXENDTC – EXSTDTC+1)] covered by visits with missing or incomplete accountability data). If the dose level of a visit is unknown, that visit should be excluded from the calculation as well in both the numerator and the denominator.

- Modal daily dose will be determined as the daily dose that is taken for the most time (in terms of number of days) among all doses taken. A subject's modal daily dose may fall in one of the categories below:
 - SEP-363856 50 mg/day
 - SEP-363856 75 mg/day
 - SEP-363856 100 mg/day
 - Tie between xx and yy (i.e. the subject was on xx mg/day and yy mg/day for the same amount of time) (if needed)

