Informed consent will be obtained from each subject before any study procedures are performed. Subjects will be evaluated for eligibility during a Screening Period of up to 21 days, during which they will continue on their pre-switch antipsychotic medication while being tapered off any prohibited medications ([Section 10.3.2](#)) in a manner that is consistent with labeling recommendations and conventional medical practices. Non-prohibited psychotropic medications other than the pre-switch antipsychotic may be continued during the study but must have been stable for at least 6 weeks prior to Screening and should be maintained at a stable dose and regimen (see [Section 10.3.1](#)).

Subjects who are being treated with two antipsychotic medications will be permitted to enter the Screening Period. At the start of Screening, the Investigator will determine which antipsychotic medication is considered “primary”, and the other one will be tapered off during the Screening Period.

Subjects who screen fail may be re-screened twice, if judged appropriate by the Investigator after discussion with the Medical Monitor. Re-screened subjects will be re-consented, assigned a new subject number, and all Visit 1 procedures will be repeated.

Open-label Treatment Period (8 weeks):

At Baseline (Day 1) (pre-switch [PS] Baseline), subjects who have successfully completed Screening and have met the eligibility criteria will begin open-label treatment with SEP-363856 while continuing to take the full dose of their pre-switch antipsychotic. SEP-363856 dosing will begin the evening of the PS Baseline visit and will continue once-daily, in the evening at bedtime, for the remainder of the Treatment Period, during which the procedures outlined in [Table 2](#) will be conducted. Subjects will be evaluated at PS Baseline and weekly throughout the rest of the study. [Section 10.3](#) describes the circumstances and specifications for which prior and concomitant psychotropic medications other than the pre-switch antipsychotic are allowed in this study.

Subjects will receive SEP-363856 50 mg/day from Day 1 through Day 3 and 75 mg/day from Day 4 through Day 7. Every effort should be made to maintain subjects at 75 mg/day from Day 4 through Day 7. Beginning on Day 8, the dose of SEP-363856 can be adjusted in increments of 25 mg among 3 dose levels (50, 75 and 100 mg), according to the following requirements:

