9.2. Study Drug Packaging and Labeling

9.2.1. Package Description

Study drug will be provided in one-week blister cards containing 9 tablets of SEP-363856 (7 days + 2 extra days).

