9.4. Dispensing of Study Drug

A Randomization and Trial Supply Management (RTSM) System (also referred to as Interactive web-based response system [IWRS]) will be used to manage subject screening and enrollment. The RTSM is an integrated web-based subject and drug management system.

Blister cards containing SEP-363856 tablets will be assigned by the RTSM based on the treatment schedule. The RTSM will generate instructions for which blister card (Medication No.) to dispense to each subject at each visit. RTSM drug dispensing guidelines should be followed for dispensing study drug to the subject. A specific user manual will be supplied.

Subjects will take one tablet of study drug per day at approximately the same time each evening at bedtime. Study drug may be taken without regard for food.

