11.9.12. Unscheduled Visit for Dose Adjustment

If a dose increase or decrease is needed between regularly scheduled visits, the subject must return to the clinic for an unscheduled visit. The following procedures will be conducted during this visit for dose adjustment:

- Study drug accountability
- Dispense study drug
- Adverse event monitoring
- Concomitant medication review

Other assessments are not required at such dose adjustment visits, but are permitted, based on the Investigator's judgment.

No dose decreases are allowed prior to Day 8.

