15.3.2. Study Drug Exposure and Compliance

Descriptive statistics on treatment exposure and treatment compliance will be summarized for the safety population.

Exposure, defined as number and percentage of subjects with ≥ 1 , ≥ 7 , ≥ 14 , ≥ 21 , ≥ 28 , ≥ 35 , ≥ 42 , ≥ 49 , and ≥ 56 days exposure, will be compiled. Descriptive statistics (n, mean, standard deviation, median, 25th and 75th percentile, minimum, and maximum) will also be calculated on exposure in days. Duration of exposure (in days) will be calculated as: last dose date - first study dose date + 1. An additional listing will also be generated to display the length of time that each subject received pre-switch anti-psychotic medication (with corresponding name and dosage).

Percent compliance will be calculated overall for the treatment period as: (number of capsules taken / number of capsules should have been taken) \times 100%. Non-compliance is defined as less than 75% or more than 125% non-missing compliance for the treatment period. Subjects with missing compliance will not be classified as non-compliant. Percent compliance will be summarized both as a continuous variable and categorically (ie. number and percentage of subjects in each compliance category: < 75%, 75% - 125%, > 125%, and missing).

Mean daily dose will be calculated for the treatment period as the cumulative dose (mg) of SEP-363856 divided by the duration of exposure (in days), where cumulative dose is the sum of all doses a subject received during the treatment period. Modal daily dose will be determined as the daily dose that is taken for the most time (in terms of number of days) among all doses taken. Both mean daily dose and modal daily dose will be summarized.

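### SAP 14.1's mean daily dose formula allows one tablet strength per visit, but the Visit 2 supply covers two, so it cannot return the protocol's cumulative dose for anyone dosed past Day 3

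*SAP*

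**What the plan says.** **The formula.** SAP 14.1 (Derivations, under Study Medication Exposure) sums over visits. Each term is one "Dose per tablet for Visit" j times the tablets dispensed less those returned and lost for that visit. The total is divided by the duration of exposure. A companion rule also treats a visit as having one dose level: "If the dose level of a visit is unknown, that visit should be excluded from the calculation as well".

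**The dosing.** Protocol 7.1, repeated in 10.1.1, states: "Subjects will receive SEP-363856 50 mg/day from Day 1 through Day 3 and 75 mg/day from Day 4 through Day 7". Protocol 9.4 adds: "Subjects will take one tablet of study drug per day at approximately the same time each evening at bedtime". Tablets come in 50, 75 and 100 mg strengths (Protocol 9.1), so a change of dose is a change of tablet. Protocol 11.9.12 states: "No dose decreases are allowed prior to Day 8".

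**The supply.** Study drug is dispensed at Visit 2 (Day 1) and next at Visit 3 (Day 8, window +2 days), per Protocol 11.9.2, 11.9.3 and Table 2. No visit is scheduled at Day 4. Cards hold nine tablets for a week (Protocol 9.2.1).

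**The target quantity.** Protocol 15.3.2 defines mean daily dose as cumulative dose over duration of exposure, "where cumulative dose is the sum of all doses a subject received during the treatment period". SAP 3.7 declares no departure from the protocol's analyses.

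**The concern.** The formula is correct only when one strength is dispensed per visit. The fixed titration breaks that condition at the first dispensing, because the Visit 2 supply has to provide both 50 mg and 75 mg tablets. A programmer who follows the text must enter one strength for that visit, and either choice gives a figure that differs from the protocol's definition.

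All subjects follow the same titration, so the error has the same direction in everyone affected and does not average out. It would also make two exposure tables disagree. SAP 14 separately tabulates days at 50, 75 and 100 mg. A completer shown there with 3, 4 and 49 days has an implied mean of 95.5 mg/day, while the mean daily dose table would show another value.

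**Working it through.** The documents state no numerical mean daily dose, so there is no figure to reproduce. The check compares the protocol's definition with the SAP formula on the same dosing history.

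**Inputs from the documents:** 50 mg on Days 1-3 and 75 mg on Days 4-7 (Protocol 7.1, 10.1.1); one tablet a day (9.4); duration = last dose date − first dose date + 1 (15.3.2, SAP 14.1).

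**Assumptions:** every dose taken; Visit 3 on Day 8; 100 mg/day from Day 8 (the level Protocol 10.1.1 aims for, subject to tolerability); 56 days of exposure for a completer.

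**Week 1 contribution**
- Protocol definition: 3 × 50 + 4 × 75 = 450 mg.
- SAP formula with 50 mg: 7 × 50 = 350 mg (−100 mg, −22.2%).
- SAP formula with 75 mg: 7 × 75 = 525 mg (+75 mg, +16.7%).
- The one value per tablet that would work is 450/7 = 64.29 mg, which is not a tablet strength and holds only with full compliance.

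**Completer, 56 days**
- Protocol definition: (450 + 49 × 100)/56 = 5350/56 = 95.54 mg/day.
- SAP formula with 50 mg: (350 + 4900)/56 = 93.75 mg/day.
- SAP formula with 75 mg: (525 + 4900)/56 = 96.88 mg/day.

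**By last dosing day (mg/day, error in brackets)**

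| Last dose | Protocol definition | Formula, 50 mg at Visit 2 | Formula, 75 mg at Visit 2 |
|---|---|---|---|
| Day 3 | 150/3 = 50.00 | 50.00 (0) | 75.00 (+25.00) |
| Day 7 | 450/7 = 64.29 | 50.00 (−14.29) | 75.00 (+10.71) |
| Day 14 | 1150/14 = 82.14 | 75.00 (−7.14) | 87.50 (+5.36) |
| Day 28 | 2550/28 = 91.07 | 87.50 (−3.57) | 93.75 (+2.68) |
| Day 56 | 5350/56 = 95.54 | 93.75 (−1.79) | 96.88 (+1.34) |

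**Range of assumptions.** From Day 7 on, the error is −100/D or +75/D mg/day for D days of exposure, whatever the later dose. For a completer on 50 mg/day from Day 8 it is still −1.79 or +1.34 mg/day, which is −3.4% or +2.6% of a mean of 51.79. If Visit 3 falls on Day 10, the Visit 2 supply covers nine days: 3 × 50 + 6 × 75 = 600 mg, against 9 × 50 = 450 or 9 × 75 = 675. The completer error is then −150/56 = −2.68 or +75/56 = +1.34 mg/day.

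**After the fix.** Summing by strength within visit gives 3 × 50 + 4 × 75 + 49 × 100 = 5350 mg, or 95.54 mg/day, which equals the protocol definition.

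**The case against.** The best defence is that the inputs come from the drug accountability log, whose layout neither document shows. Protocol 9.2.1 does not say whether the first week is one mixed card or separate cards by strength. If the log has one line per strength or kit and the program sums over lines, the result is exact. The SAP also refers to dosing start and end dates and needs days at each dose level, so dose by date must be available. This stands as a reason to expect the repair to be easy. It does not rescue the text: the written index is the visit, the companion rule speaks of a visit's dose level in the singular, and reaching the right answer means summing over something the SAP does not name.

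A second defence is that the error is small and purely descriptive. For completers this is fair: under the base assumptions it is below 2%, with no test or decision rule attached. The larger errors belong to subjects who stop in the first two weeks. These are likely to be few: SAP 3.4 cites about 7.2% discontinuing for clinical reasons, which at 101 enrolled would be about 7 (0.072 × 101 = 7.3) over the whole 8 weeks.

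Dose changes between later visits are less of a problem, because Protocol 11.9.12 requires an unscheduled visit with its own accountability and dispensing.

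**Conclusion.** The point holds as a fault in a stated formula. For any subject dosed past Day 3, SAP 14.1 as written cannot return the cumulative dose that Protocol 15.3.2 defines. The size is 1 to 3 mg/day for completers, about 5 to 11 mg/day for a stop on Day 14 (the upper figure if Visit 3 falls on Day 10: −150/14 = −10.71), and 11 to 14 mg/day for a stop on Day 7. This rests on full compliance and on applying the formula by visit. It should be corrected, but it threatens no conclusion of the trial.

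A reader might infer more than the documents support:

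- **That the dose at failure is distorted.** Mean daily dose is an average over exposure. Dose at adverse event onset is assigned from dosing dates and times (SAP Appendix 2), and adverse event summaries by dose use modal daily dose (Protocol 15.3.5.2), which counts days. Neither uses this formula.
- **That the primary endpoint or compliance is affected.** The primary endpoint counts discontinuations (SAP 17.1), and compliance counts tablets rather than milligrams (SAP 15.1).
- **That Week 1 would be dropped under the unknown-dose rule.** The Week 1 doses are fixed by protocol; two known dose levels are not an unknown one.
- **That every subject is affected.** A subject who stops by Day 3 takes only 50 mg tablets, and entering 50 mg is then exact.

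**What to change.** In SAP 14.1, index the numerator by visit and tablet strength, or by dosing or kit record, so that the 50 mg and 75 mg tablets of the Visit 2 supply are counted separately. State how returned and lost tablets from that supply are split by strength. If they are not recorded by strength, take the dose level for each day from the EX start and end dates that the SAP already uses, and say how missed doses are then handled.

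The cost is one formula and minor programming. The dosing schedule and trial conduct do not change.

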15. STUDY MEDICATION COMPLIANCE

Unless otherwise specified, the study medication compliance summary tables will include the column SEP-363856 50 to 100 mg/day.

Compliance to study medication will be presented for the SAF population, by the actual treatment group.

Document:	PPD	
Author:	PPD	Version Number: Version Date:

Percent compliance will be calculated overall for the treatment period. Non-compliance is defined as less than 75% or more than 125% non-missing compliance for the treatment period. Subjects with missing compliance will not be classified as non-compliant. Compliance will be summarized both as a continuous variable and categorically (i.e., number and percentage of subjects with compliance < 75%, 75% - 125%, > 125%, and missing).

